11.9 Secondary Efficacy Analysis: Mortality

Counts and percentages of patients who died by Day 15 and Day 28 and overall will be reported separately for each treatment arm. Separate 95% CIs (Newcombe) and p-values (Chi-Squared test without continuity correction) will be computed between SOC and treatment arms A and B.

Time to death (Day) will be reported using KM method as described on 11.3. Time to death will be calculated as follows:

Date of Death - Date of Baseline Assessment + 1.

If the patient did not die the patient will be censored at the last known date the patient is known to be still alive:

Final Date of Confirmation the patient is still alive - Date of Baseline Assessment + 1.

11.10 Exploratory Analysis: Dyspnea

The Likert scale categories (0" = no change, "1" =minimally better, "2" =moderately better, "3" =markedly better, "-1" =minimally worse, "-2" =moderately worse, "-3" =markedly worse) will be reported using counts and percentages at all scheduled timepoints for all treatment arms and overall.

11.11 Exploratory Analysis: Cough VAS and D-dimer

Percentage of change from baseline (defined in 3.2), change from baseline and actual values of Cough VAS and D-dimer at all scheduled timepoints will be summarized using continuous descriptive statistics (defined in 3.1) for all treatment arms and overall. T-test assuming unequal variance p-values and 95% CI comparing the differences between SOC and treatment arms A and B will also be provided for the percentage of change analysis.

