#### **7.4.10.2 VAS Questionnaire**

Cough severity will be measured using a 0-100mm Visual Analog Scale (VAS) from “no cough” to “worst cough ever.”

A copy of the VAS Questionnaire can be found in [Appendix 16.3](#).

Note: the site should hand out the Visual Analogue Scale (VAS) to the subject for completion. If this is not possible, any alternative administration of the VAS must be documented clearly in the source. Reasons for an alternative method may include e.g. site policy to avoid document contamination, or a visually impaired subject. The following alternative options are accepted:

- Subject pointing to the VAS with some device and another person adding the line for them.
- If this is not possible, the subject can rank the score 0 – 100 (as the VAS line is 100mm). Site should hold up the VAS in front of the subject and/or describing this to try and retain some visual aspect.

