3.2 General Key Definitions

The following definitions will be used:

- Date of the First Study Treatment Administration: The date of the first study treatment administration is defined as the earliest date on which a study treatment was administered.
- Date of the Last Study Treatment Administration: The date of the last study treatment administration is defined as the latest known date on which a study treatment was administered.
- Baseline: The Baseline value is value taken on Day 1. If Day 1 value is missing, Baseline is defined as the last available valid, non-missing observation for each patient prior to first study treatment administration on Day 1. Repeat and unscheduled assessments will be included in the derivation of the Baseline values only if Baseline visit value is missing.
- Change from Baseline: The absolute change from Baseline value is defined as the difference between the result collected/derived at a post-baseline visit and the Baseline value.

The change from Baseline value at each post-baseline visit will be calculated for all continuous parameters using the following formula:

$$\text{Change from Baseline Value} = \text{Result at post-baseline visit} - \text{Baseline Value}$$

The change from Baseline value will only be calculated if the specific post-baseline visit result and the Baseline value for the parameter are both available and will be treated as missing otherwise. In the data listings, the change values will be set to '-' (not applicable) for pre-baseline assessments.

The rate of change from baseline is defined as: Change from Baseline value/Baseline Value

- Study Day: The study day of an event is defined as the relative day of the event starting with the date of the first study treatment administration (reference date) as Day 1 (there will be no Day 0).

The study day of events occurring before the first study treatment administration will be calculated as:

$$\text{Study Day} = (\text{Date of Event} - \text{Date of First Study Treatment Administration})$$

For events occurring on or after Day 1, study day will be calculated as:

$$\text{Study Day} = (\text{Date of Event} - \text{Date of First Study Treatment Administration}) + 1$$

Study days will only be calculated for events with complete dates and will be undefined for events that are 'Ongoing' at the end of the study.

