3.3 Handling of Missing Data

All data will be analysed as collected and missing values will not be imputed or replaced unless stated otherwise.

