11.7 Secondary Efficacy Analysis: Oxygenation

11.7.1 PaO₂ and PaO₂/FiO₂

Continuous data descriptive statistics (3.1) for PaO₂ and PaO₂/FiO₂, change from baseline, percentage of change from baseline in accordance to 3.2 will be reported for each treatment arm at all scheduled visits. T-test assuming unequal variance p-values and 95% CI comparing the differences between SOC and treatment arms A and B will also be provided for percentage change from baseline analysis.

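### PaO2, PaO2/FiO2, cough VAS and D-dimer are tested by unadjusted t-tests on percent change: valid, but usually less efficient than a baseline-adjusted model, and unable to include a patient whose baseline cough VAS is 0

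*SAP*

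**What the plan says.** SAP 11.11 plans, for cough VAS and D-dimer, "T-test assuming unequal variance p-values and 95% CI comparing the differences between SOC and treatment arms A and B", and says these "will also be provided for the percentage of change analysis". SAP 11.7.1 uses the same test for PaO2 and PaO2/FiO2, where the results "will also be provided for percentage change from baseline analysis".

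The underlying summaries cover every visit. For PaO2 and PaO2/FiO2 they "will be reported for each treatment arm at all scheduled visits"; for the other two, "actual values of Cough VAS and D-dimer at all scheduled timepoints will be summarized". Neither section names a covariate or a repeated-measures model.

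SAP 3.2 supplies the response: "The rate of change from baseline is defined as: Change from Baseline value/Baseline Value". It has no rule for a baseline of zero, and under SAP 3.3 "missing values will not be imputed or replaced unless stated otherwise".

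Elsewhere the SAP does more. Randomization is stratified by site and age (SAP 2.6). Both factors are in the primary model (11.1), the Cox and Fine-Gray models (11.3) and the mixed models for WHO-7 (11.4.2) and NEWS (11.5.2). The WHO-7 model also includes baseline and a day-by-arm interaction. Viral load is log10-transformed (11.12); D-dimer is not.

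Protocol 10.9.2 plans only a descriptive summary of cough VAS.

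**The concern.** Dividing by a noisy baseline adds variance to the response. It also makes the response right-skewed when the measure itself is skewed, as D-dimer can be expected to be. A t-test on that ratio uses the baseline, but not efficiently, and takes no account of age or site.

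The cough VAS runs from 0 to 100 mm, with 0 meaning no cough (Protocol 7.4.10.2). A patient with no cough at entry has no percent change and drops out of an analysis labelled ITT. A baseline of a few millimetres gives percentages large enough to dominate the arm mean.

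At stake is the sensitivity of a small pilot. SAP 2.1 says Phase 2b data will be used to select and rank secondary endpoints for Phase 3, and PaO2 and PaO2/FiO2 are among them. With about 50 patients per arm, and fewer at in-hospital visits, an inefficient test can make a responsive endpoint look unresponsive. Cough VAS and D-dimer are exploratory and carry less weight.

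**Working it through.** **1. The plan's own figure.** The only power-based number is the Phase 3 total for the ordinal primary endpoint. Whitehead's formula with the SAP Table 2 distributions is N = 12(z₀.₉₇₅ + z₀.₉₀)² / [(ln OR)²(1 − Σp̄³)]. With z-sum 1.960 + 1.282 = 3.242, ln 1.75 = 0.5596 and Σp̄³ ≈ 0.126, this gives 126.1 / (0.3132 × 0.874) ≈ 461, or 462 as two equal groups. That reproduces. So do the enrolment figures: 462/0.9 = 513.3, up to 514; and 50/0.9 = 55.6, up to 56 per arm, × 3 = 168. No SD, correlation, target difference or power is stated for the four measures here.

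**2. Change score against ANCOVA, analytically.** With equal variances and correlation ρ between baseline and follow-up, the variance ratio of a plain change score to ANCOVA is 2(1 − ρ)/(1 − ρ²) = 2/(1 + ρ). Where ANCOVA has 80% power, the change score has Φ(2.80/√ratio − 1.96).

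| ρ | Variance ratio | Change-score power |
|---|---|---|
| 0.3 | 1.54 | 62% |
| 0.5 | 1.33 | 68% |
| 0.7 | 1.18 | 73% |
| 0.9 | 1.05 | 78% |

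Dividing by baseline can cost more than this when the coefficient of variation (CV) is large.

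**3. Percent-change Welch test against ANCOVA, simulated.** Inputs from the documents: 50 per arm, two-sided 5%. Everything else is assumed. There were 4,000 trials per setting (simulation error at most 0.8 points per power). ANCOVA adjusts for baseline only, so nothing is credited for age, site or repeated measures.

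*D-dimer*: log-normal, 30% reduction, ANCOVA on the log scale.

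| Log-SD | ρ | Percent-change test | ANCOVA | Loss (points) |
|---|---|---|---|---|
| 0.8 | 0.4 | 38.1% | 66.4% | 28.3 |
| 0.8 | 0.6 | 57.6% | 78.0% | 20.4 |
| 0.8 | 0.8 | 89.8% | 95.2% | 5.4 |
| 1.0 | 0.4 | 22.9% | 47.5% | 24.6 |
| 1.0 | 0.6 | 38.0% | 58.9% | 20.9 |
| 1.0 | 0.8 | 71.4% | 82.6% | 11.2 |

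*PaO2/FiO2*: (a) mean 200, SD 60, values floored at 60, difference 40; (b) log-SD 0.3 with a 20% proportional effect, ANCOVA on the log scale.

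| ρ | (a) test / ANCOVA | Loss | (b) test / ANCOVA | Loss |
|---|---|---|---|---|
| 0.3 | 61.7% / 93.0% | 31.3 | 69.0% / 88.0% | 19.0 |
| 0.5 | 77.4% / 96.0% | 18.6 | 82.7% / 93.2% | 10.5 |
| 0.7 | 94.5% / 99.6% | 5.1 | 96.8% / 98.6% | 1.8 |
| 0.85 | 99.8% / 100.0% | 0.2 | 100.0% / 100.0% | 0.0 |

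Separate runs moved individual losses by 1 to 3 points; the ranges in the verdict cover them.

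*Cough VAS*: 0–100 score, assumed baseline mean 30 to 50 and SD 20 to 25, ρ 0.3 to 0.7. Between 0.6% and 12% of patients have no percent change. Power is 35–78% for the t-test against 81–88% for ANCOVA of the score.

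**4. Size of the test.** With no effect, the percent-change test rejected in 4.0–5.6% of trials in the D-dimer and PaO2/FiO2 settings, and in 2.7–5.3% over a wider grid of correlations and CVs. It is not inflated, and is sometimes conservative.

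**5. Scale matters.** With a proportional effect, CV 0.4 and ρ 0.9, percent change (76%) beat ANCOVA on the raw scale (73%), while log-scale ANCOVA had 79%. For D-dimer the log is therefore part of the repair.

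**The case against.** The strongest reply is that these are valid tests of secondary and exploratory measures in a pilot that SAP 11.1 itself calls exploratory, so little rides on their power. Validity and low stakes both stand: this is a point about efficiency and interpretation.

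Four stronger readings are tempting, and the documents do not support them.

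- *A reader might infer that the t-tests drive the interim.* SAP 14.1 lists the interim PaO2 output among descriptive statistics. The later ranking of endpoints in SAP 2.1 is tied to no p-value.
- *A reader might infer that the oxygenation series gets no adjusted analysis.* SAP 11.7.3 and 11.7.4 plan time to a PaO2 of 80–100 mmHg and time to a PaO2/FiO2 above 400 mmHg, with death as a competing risk. SAP 11.3 analyses these by a Fine-Gray model with age and site. That answers part of the concern, although 11.3 also withdraws a time-to-event analysis if any patient had the event before randomization.
- *A reader might infer that all four measures fail at a zero baseline.* PaO2 and PaO2/FiO2 cannot be zero, and a low D-dimer is at most below a quantification limit. Only cough VAS is affected in practice.
- *A reader might quote a drop such as 66% against 96% for PaO2/FiO2 as the cost.* That comes from setting (a) at ρ = 0.5 without the floor, where near-zero simulated baselines inflate the ratio. With the floor it is 77% against 96%.

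It is also fair that omitting age and site is not unique to these sections: the SAP's chi-squared comparisons are unadjusted too. The contrast is with its regression models.

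**Conclusion.** The point holds as one of efficiency. The four comparisons are valid, usually less powerful than a baseline-adjusted analysis, inconsistent with the SAP's own models on age and site, and undefined for a cough VAS baseline of 0.

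No single loss can be stated, because the documents give no correlation, spread or target effect. Under the assumptions above, D-dimer loses about 4 to 28 points over correlations 0.4 to 0.8. PaO2/FiO2 loses about 19 to 32 points at correlation 0.3, 8 to 19 at 0.5 and almost nothing at 0.85. All of this takes 50 patients per arm at the visit tested. Assessments on Days 2 to 14 are made only while the patient is in hospital, so actual numbers and power at those visits will be lower for either method. The primary endpoint is not touched.

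**What to change.** - **PaO2 and PaO2/FiO2 (SAP 11.7.1).** Replace the per-visit t-tests with the SAP 11.4.2 mixed model: baseline, arm, day, arm-by-day, age and site, over all scheduled post-baseline days including Day 29. State that it uses each patient's values up to discharge but does not by itself remove informative discharge or death. Protocol 7.4.10.1 allows a reduced set of PaO2 days, so some daily values will be missing. Keep the time-to-event analyses.
- **D-dimer (SAP 11.11).** Use ANCOVA on the log scale, or the same mixed model on the log scale, with baseline, age and site. Say how values below a quantification limit enter the log; the substitution in SAP 12.3 covers only limits of at least 1. Per-visit ANCOVA would still include only patients in hospital at Days 3 to 11, and the SAP should say so.
- **Cough VAS (SAP 11.11).** Reconcile the planned test with the descriptive-only plan in Protocol 10.9.2. If a test is kept, analyse the absolute score adjusted for baseline, age and site, so that a zero baseline is usable.
- **Percent change.** Keep it as a descriptive summary for all four, reporting how many patients have no value because the baseline is 0.

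The cost is a few SAP sentences and standard code, much of it already in SAP 11.4.2. No new data are needed.

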11.12 Exploratory Analysis: Qualitative and Quantitative PCR SARS-Cov-2

Counts and percentages for type of sample (nasal, nasopharyngeal, oropharyngeal, blood and other) for qualitative and quantitative PCR SARS-Cov-2 will be provided for all treatment arms and overall at all scheduled time points.

Continuous data involving log 10 transformed quantitative viral RNA load results and change from baseline will be reported in accordance to 3.1 for all treatment arms and overall at all scheduled time points.

11.13 Cytokine Marker Results

The following Cytokine marker will be taken at the time points specified in the study procedure schedule (section [Table 1](#)):

- IFN γ
- GM-CSF
- IL-6
- IL-12
- TNF-alpha

Summary statistics for cytokine markers in accordance to [section 3.1](#) will be presented for baseline and for each scheduled pre and post-baseline visit (which also includes change from baseline, clinical significance) where applicable. These summary tables will be done for ITT and PPS populations for treatment groups defined in [section 3.4](#).

All information related to cytokine marker (cytokine marker type, result, reasons not done, date and time of sample collection) will be presented in the by-participant data listings by treatment arm (grouping provided in [section 3.4](#)) sorted by patient ID and visit for the Safety population, along with the age and sex and baseline weight of the patient.

12. SAFETY

All Safety endpoints will be analysed using the Safety analysis set.

12.1 Dose Limiting Toxicity

The occurrence of any of the following toxicities from the initial dose of Ifenprodil administration (in combination with Standard of Care (SOC)) which results in:

- a. The necessity to delay ifenprodil administration in the participant, OR
- b. To reduce the dose of ifenprodil administered, either for the participant, or for subsequent participants,

will be considered a DLT, if judged by the investigator to have a reasonable possibility of being related to the ifenprodil administration.

Severity is graded according to the NCI Common Terminology Criteria for Adverse Events (CTCAE), Version 5.0 equivalents of mild, moderate or severe:

1. Grade 3 or higher toxicity, except elevations in gamma-glutamyltransferase (GGT)
2. Grade ≥ 3 AST/ALT elevation
3. Grade ≥ 2 AST/ALT elevation with Grade ≥ 2 bilirubin elevation

Dose Limiting Toxicity will be identified in AE listings.

12.2 Adverse Events

All AE verbatim terms will be coded using the Medical Dictionary for Regulatory Activities (MedDRA) version 21. Chest X-ray resulting in AEs will also be reported. Treatment Emergent Adverse Events (TEAEs) are all events which start or worsen after the first dose of study drug up to and including the follow up period. If missing dates or time prevent a clear determination as to whether the AE is treatment emergent, the adverse event will be regarded TEAE. If a patient experienced the same adverse event multiple times, this will only be counted once for the purpose of counting the number of patients experiencing that adverse event. For the SOC arm, all AEs are considered TEAEs.

An overall summary of TEAEs for counts and percentages by treatment groups defined in [section 3.4](#) will be provided for the following items:

- Any TEAE
- Any Serious TEAE
- Any type of serious TEAE (Result in Death, Immediately Life-Threatening, Inpatient hospitalization or prolongation of existing hospitalization, Persistent or Significant Disability or Incapacity, Congenital abnormality or birth effect, Important Medical event may require medical intervention to prevent events above)
- Any TEAE grade (intensity) experienced (Mild [Grade 1] Moderate [Grade 2] Severe [Grade 3] Life-Threatening [Grade 4] Fatal [Grade 5])
- Worst TEAE grade (intensity) experienced (Mild [Grade 1] Moderate [Grade 2] Severe [Grade 3] Life-Threatening [Grade 4] Fatal [Grade 5])
- Action taken (None, Medication Given, Procedure/Intervention Needed, Other)
- Action taken for Ifenprodil (Dose discontinuation, Drug interrupted, Unknown, None, Not Applicable)
- Action taken for SOC (Dose discontinuation, Drug interrupted, Unknown, None, Not Applicable)
- Outcome of TEAE (Recovered/Resolved, Recovering/Resolving, Recovered/Resolved with Sequelae, Not recovered, Death, Unknown, Patient discontinued from study)

- Relationship to Ifenprodil/SOC (Reasonable Possibility, No Reasonable Possibility, Not Applicable)

The following table summaries (counts, percentages and number of events) will be presented by System Organ Class and Preferred Term by treatment arm (defined in [section 3.4](#)):

- Summary of TEAEs
- Summary of Serious TEAEs.
- Summary of TEAEs (grade 1 or 2).
- Summary of TEAE (grade of 3 or more)
- Summary of Ifenprodil related TEAEs (applicable to Arm A and B only)
- Summary of SOC related TEAEs (applicable to all treatment arms)
- Summary of Ifenprodil related Serious TEAEs (applicable to Arm A and B only)
- Summary of SOC related Serious TEAEs (applicable to all treatment arms)
- Summary of TEAEs Leading to Study Discontinuation.
- Summary of TEAEs Leading to Death.

All AEs will be listed and will include the start and stop date of AEs, AE number, verbatim term, Preferred Term, System Organ Class, treatment, SAE/Type, TEAE, actions taken for AE, actions taken with SOC/Ifenprodil, causality to SOC/Ifenprodil and outcome. Separate listings will be created for SAEs. These listings will be presented by treatment arm (grouping provided in [section 3.4](#)) sorted by patient ID and AE start date for the Safety population, along with age, sex and baseline weight of the patient.

12.3 Safety Laboratory Assessments

The following laboratory measurements will be taken at the time points specified in the study procedure schedule ([Table 1](#)):

- 1) Hematology: Hemoglobin, hematocrit, white blood cell counts, including differential, platelet count, red blood cell count, myoglobin
- 2) Biochemical tests: Glucose, blood urea nitrogen (BUN), serum creatinine, sodium, potassium, chloride, bicarbonate, alanine aminotransferase (ALT), aspartate aminotransferase (AST), alkaline phosphatase (ALP), gamma glutamyl transpeptidase (γ -GT/GGT), total bilirubin, calcium, phosphorus, albumin, total protein, uric acid
- 3) Coagulation: activated partial thromboplastin time (aPTT) prothrombin time (PT), international normalised ratio (INR), D-dimer.
- 4) Urinalysis: Specific gravity, hydrogen ion concentration (pH), protein, glucose, bilirubin, ketone, urobilinogen, blood, leukocytes, casts, bacteria.

In some instances, continuous variables are expressed as a range (i.e. < 10). In such cases, as long as the limit of quantification is at least 1, values may be converted to the range boundary (upper or lower limit as applicable) by subtracting or adding the smallest whole number of the limit of quantification. As an example, a value of <10 may be converted to 9. A value of > 100 may be converted to 101. Such substitutions will be clearly documented in the footnotes of relevant outputs.

For the hematology, blood coagulation, chemistry, continuous and discrete (low, normal, high) data summary statistics (as described in [section 3.1](#)) will be presented for values and change from baseline value/shift from baseline at each visit. For urinalysis, discrete data summary statistics on categorical results (as described in [section 3.1](#)) will be presented for values at each visit. For pH the result will be

classified into <5, 5 to 8 and >8. For Specific Gravity, the result will be classified into ≤ 1.015 , 1.061 to 1.021, 1.021 to 1.025, 1.026 to 1.030 and > 1.030 . For Urobilinogen, the result will be classified into ≤ 1 mg/dL, 1 mg/dL to < 2 mg/dL and > 2 mg/dL. These summary tables will be done for Safety population for treatment groups defined in [section 3.4](#)

The listings of laboratory parameters (hematology, chemistry and urinalysis) will include all the information collected. In addition, the observations that are used as the baseline record (value) for each parameter will be flagged, and the change from baseline values (where applicable) at each pre and post baseline (scheduled and unscheduled) visit will be presented, along with reasons for laboratory assessments not done. These listings will be presented by treatment arm (grouping provided in [section 3.4](#)) sorted by patient ID and visit for the Safety population, along with age, sex and baseline weight of the patient.

12.4 Vital Signs

The following vital signs measurements will be taken at the time points specified in the study procedure schedule (section [Table 1](#)):

- Systolic blood pressure (SBP) (mmHg)
- Diastolic blood pressure (DBP) (mmHg)
- Pulse Rate (beats/min)
- Respiratory rate (breaths/min)
- Body Temperature ($^{\circ}$ C)
- Oxygen Saturation SpO₂ (%)
- Level of Consciousness (Alert, Arousable only to voice, Arousable only to pain, Unresponsive)
- Presence of clinically significant result

Summary statistics for vital sign parameters in accordance to [section 3.1](#) will be presented for baseline and for each scheduled pre and post-baseline visit (which also includes change from baseline, clinical significance) where applicable. These summary tables will be done for Safety population for treatment groups defined in [section 3.4](#).

The listing of vital sign parameters will include all the information collected. In addition, the observations that are used as the baseline record (value) for each parameter will be flagged, and the change from baseline values at each pre and post baseline (scheduled and unscheduled) visit will be presented along with whether the result was clinically significant (AE/MH numbers if applicable) and reasons not done. This listing will be presented by treatment arm (grouping provided in [section 3.4](#)) sorted by patient ID and visit for the Safety population, along with the age and sex and baseline weight of the patient.

12.5 12-Lead Electrocardiogram (ECG)

The following ECG measurements will be taken at the time points specified in the study procedure schedule (section [Table 1](#)):

- Ventricular HR (beats/min)
- PR interval (msec)
- QRS interval (msec)
- ST segment (msec)
- QTcF interval (msec)
- Presence of clinically significant result (normal, abnormal not clinically significant, abnormal and clinically significant)

Summary statistics for 12-Lead ECG parameters in accordance to [section 3.1](#) will be presented for baseline and for each scheduled pre and post-baseline visit (which also includes change from baseline). These summary tables will be done for Safety population for treatment groups defined in [section 3.4](#)

The listing of 12-Lead ECG parameters will include all the information collected (including an overall assessment of presence of clinically significant result). In addition, the observations that are used as the baseline record (value) for each parameter will be flagged, and the change from baseline values at each pre and post baseline (scheduled and unscheduled) visit will be presented along with whether the result was clinically significant (AE/MH numbers if applicable) and reasons not done. This listing will be presented by treatment arm (grouping provided in [section 3.4](#)) sorted by patient ID and visit for the Safety population, along with the age and sex and baseline weight of the patient.

